### **Orientation to the Program (see Appendix Q)**

Each participant leaves with his/her assessment form.

Intervention group meets with [name] who: Completes the Goals Form based on the assessment form and patient input. [name] will put copy in binder and make copy for records. [name] will document PT progress note with plan of care and goals in medical record (Initial evaluation was done by outpatient physical therapist).

Review program

Review program goals and baseline assessment results

Define falls

Discuss how to handle symptoms, falls.

Provide the activity monitor, teach use

Identify if safe for walking program

Orient to the Activity log; Ask participants to log steps/day, symptoms, falls.

Review calendar for future data collection, 3 month booster session, 6 month data collection.

### **Healthy YOUiversity**

The Healthy YOUiversity instructor ([name]) will conduct an orientation that will consist of an explanation of the overall structure of the class, the calendar, and provision of the participant binder, providing our definition for falls, documentation of their exercise, falls and adverse events, and how to contact study staff.

## **Data Collection during the Program**

The instructors will record attendance, and copy the Action plans/tracking sheets as record of exercise adherence, falls and adverse events. See above for procedures related to Adverse events.

### 6 Week Data Collection Assessment (See Appendix S)

Both Groups		Intervention Only	Control Group Only
Performance-based	Self-Report		
4-stage Balance	LLFDI community mobility short form or CAT		
TUG	FES-I		
30-second Chair Stand	ABC-6		
DGI	Barriers Self-Efficacy		
	Get up from floor		
	Exercise Adherence: walking, strength, balance (from Action Plan/Tracking doc)	6-wk Intervention program evaluation questions	6 week Healthy YOUiversity program evaluation questions
	Falls (from Action Plan/Tracking doc)		
	Adverse Events (from Action Plan/Tracking doc)		

### 3 Month Data Collection (See Appendix T)

Both Groups		Intervention Only
Performance-based Measures	Self-report Measures	
4-stage balance	LLFDI community mobility short form or CAT	
TUG	FES-I	
30-second Chair Stand	ABC-6	
DGI	Barriers Self-Efficacy	
	Get up from floor	
	Exercise Adherence: walking, strength, balance	
	Falls (from Action Plan)	
	Adverse Events (from Action Plan)	
	Falls Questions	Peer-Coaching Questions (Full)

**6 Month Data Collection (See Appendix U)**

Both Groups		Intervention Only
Performance-based Measures	Self-report Measures	
4-stage balance	LLFDI community mobility short form or CAT	
TUG	FES-I	
30-second Chair Stand	ABC-6	
DGI	Barriers Self-Efficacy	
	Get up from floor	
	Steps/Day	
	Exercise Adherence Walking, Strength, Balance	LIFT program overall questions
	Falls questions	Peer-Coaching Questions (full)

A summary of the program content is provided below.

	Exercise	Goal-Achievement
Week 1		
Class 1	Time: 45 min	15 min
	Content: Learn warm up, strength, balance and flexibility ex's, overall ex goals (2-3X/week: 2-3 sets 70% 1 RM; balance challenge, walking 3x/week), estimating 70% 1RM; safety, logging activity, symptoms, falls	Group building/Ice-breaker activities Homework: Look at the Action Plan
Class 2	45 min	15 min
	Learn warm up, strength, balance and flexibility ex's, overall ex goals (3X/week: 1 set of 10 70% 1 RM; balance challenge, walking 3x/week), estimating 70% 1RM; safety, logging activity, symptoms, falls	Work on Action Plan Introduction to Self-awareness
Week 2		
Class 3	45 min	
	How to progress activity (PT to determine by self-report of PEI and if able to perform 2 sets of resisted exercises progression of weight. Determine safety of decreasing support with balance and standing exercises.	15 minutes
		Problem-solving skills
		Self-awareness
Class 4	45 min Warm up, strengthening exercises, flexibility, balance exercises with progression of decreasing support	15 minutes
	Ramp/stairs	Self-Assessment
	Introduce methods of transferring safely to floor and up with modifications	
Week 3		
Class 5	30 min Warm up, strengthening exercises, flexibility, balance exercises with progression of decreasing support.	15 min Problem-solving
		15 minutes peer coaching
		Video; fall-specific coaching; roles and responsibilities
Week 4		
Class 6	30 min Encourage participants co-lead exercises. Warm up, strengthening exercises, flexibility, balance exercises with progression of decreasing support	30 min
	Set up obstacle course with foam, rocker board, static balance challenges, steps, reaching with and without UE support	Peer-coaching skills (active listening)
		Break-out in pairs
		Report back
Week 5		

	Exercise	Goal-Achievement
Class 7	30 min Warm up, strengthening exercises, flexibility, balance exercises with progression of decreasing support	30 min
	Incorporate dynamic balance training including head turns, change in gait speed, turning, stepping over objects.	Intro 2 groups of 4
	Practice standing to floor transfers as appropriate	Planning your conversation with peers
		Breakout in 4s; Try it; Debrief
		Method of contact; Schedule of calls and facilitator
Week 6		
Class 8	30 min Encourage participant co-lead Warm up, strengthening exercises, flexibility, balance exercises with progression of decreasing support. Determine progression of weights and support for balance exercises for final class and progression at home.	30 min
		Review how the meeting went
		Self-assessment
		Peer-coaching
		Set up goal for 1 month
Week 12	30 min Discuss present program; review recent flow chart for home exercise program; review exercise intensity levels based on the Perceived Exertion Rating for each exercise type (e.g. resistance and walking). Individual progression and/or modifications will be determined by the physical therapist.	The Goal-Setting program lead will facilitate a discussion about how goal-setting and peer-coaching activities have been going.

## **Statistical Analysis Plan**

### **From grant submission 7-27-2015**

Enrollment and safety data will be collected in the study database by the clinical co-investigators. Safety analyses will be conducted based on similarly basic data collection and tracking and will include summary falls, adverse events and protocol deviations, and summary statistics (n,%) calculated. This feasibility study will not be powered to detect differences in outcomes between the 2 groups. We will carefully examine baseline rates of falls and other variables to enable rigorous sample size calculations for a formal clinical trial. However, preliminary analyses of changes in the intervention and control groups will be assessed to inform study planning. We will calculate the means and standard deviations at pretest (baseline) and corresponding values at post-tests (6-week/program completion, 3-month post program, 6-month post program). The corresponding confidence intervals will be calculated to fully describe the plausible true population values. We will explore differences between the intervention and control group in baseline characteristics, and relationships between these variables and outcome variables of interest. Differences between the groups will inform planning for randomization and baseline values may be used to adjust for differences in our preliminary analyses of differences between groups. At each post-test time point, we will apply analysis of covariance (ANCOVA) to examine the relationship between the post-test score and treatment controlling for the pretest score and demographic variables.

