The proposed project, Living In Fitness Together (LIFT) tests the feasibility and preliminary efficacy of a group-based PT fall prevention program using a within-group peer coaching intervention to improve outcomes for older adults at risk for falls by promoting sustained patient engagement in exercise and physical activity. The program will consist of group-based physical therapy for balance, strength, flexibility, and mobility training combined with a behavioral theory-based goal-achievement and peer-coaching training intervention targeting self-efficacy for the patients/group participants. It consists of 8 group sessions over 6 weeks plus one group booster session delivered by a physical therapist (PT) and trained staff. The program is designed to: 1) deliver progressive, tailored, and challenging exercise intervention for older adults at risk for falls; 2) empower older adults to achieve the required milestones for exercise and physical activity through training in theory-based behavior change, self-management, peer support and peer-coaching applied among the group participants; 3) incorporate evidence-based home safety intervention with necessary support for implementation of modification recommendations. By focusing on peers empowering each other within PT intervention as the center of exercise-based fall prevention for long-term patient engagement, this project will provide an innovative model for successful fall prevention.

Our Specific Aims are to:

1. Assess the feasibility of implementing the peer-coaching program in the physical therapy practice context by measuring enrollment, attendance, and completion of the program.
2. Evaluate whether the LIFT Fall Prevention program creates long-term behavior change as measured by exercise adherence at 6 months.
3. Evaluate safety and preliminary efficacy of the LIFT Fall Prevention program among 48 patients within an outpatient physical therapy practice. Safety will be assessed using self-reported falls, injuries, and adverse events. To support trial design for a future comparative

trial, we will measure indicators of initial efficacy including lower extremity strength and function, balance, balance confidence, concern about falls, mobility, physical activity, self-efficacy for exercise, and exercise adherence.

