## **Self-Assessment**

Self-Assessment will be framed as dialogue with oneself, with peer coaches, or other sources of social support. The approach is aimed at fostering experiential learning and development of self-efficacy for exercise. A key feature of the training will be the focus on teaching participants to model the target behaviors in their group interactions. We will train participants to ask and answer key questions to assess their progress, build self-efficacy, problem-solve, and take positive action to achieve their goals (Appendix C).

Sample questions include:

- What went well? Did I do the exercises and activity I planned?
- What were my challenges? [Impediments/barriers]
- What are some solutions I could try/What could I do next time?
- Which one(s) will I try first?

Participants will use these questions to foster problem solving with an emphasis of experimentation, and solution focused success. Participants will be encouraged to write out their responses to the questions and to share with the group. If they report success then they

will be demonstrating good role modeling for the group. If they report barriers, then the group can help with group problem solving, by practicing brainstorming. They will identify the barrier(s), pick one, then brainstorm with the group and lastly chose one to try during the coming week. These steps will be repeated weekly by all participants to encourage experiential learning, self-efficacy and adherence to their exercise program and incorporated into their interaction in the peer-support sessions.

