**Peer-Coaching Component**

[figure not shown]
The goal of the Peer coaching component is for team members to provide social and emotional support to each other to support achievement of the exercise adherence goals. Peer coaching is a process in which 2 or more team members work together to implement their individual exercise Action Plans by modeling problem-solving and social and emotional support skills. This process includes sharing feelings, successful experiences, challenges, ideas, and results of personal experiments, and reinforcing skill achievement. In LIFT peer coaching is conducted by the participants themselves, rather than graduates or older adults who have succeeded in long-term adherence to exercise. The emphasis of the LIFT program is on learning adherence and peer support skills together.

Participants will receive instruction and training in roles and responsibilities and basic peer support skills including active listening, such as restating, summarizing, minimal encouragers, reflecting, giving feedback, using simple follow-up questions, validation, effective pause, and avoiding communication blockers. We will also teach the use of open and closed-ended questions. This material will be taught using lecture, discussion, video as well as role playing in which the participants will practice specific skills in multiple group sizes (pairs, and groups of 4) in the context of their own exercise goals. We will ask participants about their current technology use and incorporate technology as appropriate, including group calls and social media. We will

teach the participants how to conduct a group call/session, and how to fulfill the role of facilitator.

Support materials such as scripts and choices of probes are provided in the LIFT binder. Participants will have the opportunity to debrief after they practice the skills, and after they try peer-coaching on their own. They will be provided with contact information for the research team for questions or problems. Figure 4 below provides a detailed model of the elements of the Goal Achievement component.

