## **Individualized PT Goals for Participant**

### Long Term Goals (12 weeks)

1. Participant demonstrates knowledge and understanding of components of home exercise program (flexibility, strengthening and endurance) including progression, proper technique and modifications. They will demonstrate proper and safe use of adjustable leg weights and pedometer.
2. Participant will meet the following goals :
  - a. Walking 7,000-10,00 steps 3 or more days/week
  - b. Perform strengthening exercises 3 days/week
  - c. Perform balance exercises 3 or more days/week
  - d. The total exercise goal per week will be at least 2 hours
3. Participant will meet personal functional goal as established at start of program.
4. Peer coaching goal: Participants will connect via phone or social media 1-2x weekly with a member of their peer coaching team.

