## Control Program

The control group will continue with "usual care" one-on-one physical therapy. In addition, they will attend a control group class that provides social interaction and interesting health information. They will be asked to track when and how much they do their PT home exercise program, walking, and any falls or adverse events or problems. Below is a description of the control group class.

**"Healthy YOUiversity"** is a program developed by Boston University and Mt Ascutney Hospital and Health Center (MAHHC) for the Living In Fitness Together Research Study to provide group education about activities and behaviors that promote healthy living. This 6-session program includes the following topics:

**Home Safety:** Content will be provided in the participant binder to address the range of ways to enhance safety inside and outside of the home. This content will be reviewed in the orientation session so that questions can be answered and participants can expect the OT's call. A Home Safety Assessment by an Occupational therapist will be offered, as described above in the Home Safety Assessment section.

**Session 1. New Stress Paradigm.** This session will discuss stress within the context of the Energy In - Energy Out paradigm. Participants will learn examples of healthy activities and choices across a range of topics including nutrition, sleep, positive thinking, social support, meaningful activities, and exercise. Activities and choices that may deplete energy and overall health will be discussed. Tools such as visual imagery, mindfulness, breathing exercises, and simple techniques to enhance healthy sleeping patterns will be presented. Handouts will be provided in the participant binder.

**Session 2. Nutrition.** This session will teach the heart healthy diet as outlined by The American Heart Association, National Institutes of Health and the American Medical Association. Handouts from government websites will be provided in the participant binder.

**Session 3. Leisure Education for Quality of Life.** This session will explore the PLESS approach to including a variety of healthy leisure activities.

- **P:** Physical
- **I:** Intellectual
- **E:** Emotional/Relaxing
- **S:** Social
- **S:** Spiritual/Meaningful.

**Session 4. Social Capital** This session will define social capital and how it aids a healthy lifestyle. Examples will be discussed including sharing information and resources, providing assistance, and building trust.

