### **Enrollment**

Study staff will call the patient to provide information on the study, answer questions and set up a time to enroll, likely before or after the next physical therapy session. At that session, study staff will provide specific information on the class meeting times and commitment, and clarify that the start date is to be determined when all 16 participants have been enrolled. She will obtain written, informed consent, and let the participant know that study staff will call them about when the program will begin. [name] will complete the Master Key document (Appendix M), assigning the participant a study identification number (study ID). The study ID will be used to identify the participant in the consent form and data collection forms.

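### The planned ANCOVA ignores the group delivery of LIFT; if outcomes correlate within LIFT classes, the standard error of the arm difference is modestly too small (minor)

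*Combined protocol and SAP*

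**What the plan says.** The only between-arm model in the Statistical Analysis Plan is an ANCOVA at each post-test. The SAP will "apply analysis of covariance (ANCOVA) to examine the relationship between the post-test score and treatment controlling for the pretest score and demographic variables". It names no class, peer-team or wave term, and clustering is not mentioned anywhere in the combined document. The same section says that the study is not powered for differences between the arms and that the comparisons are preliminary, for planning. It plans confidence intervals around the means, without a stated level, and does not explicitly plan one for the ANCOVA arm difference.

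The intervention is described as a group process. The Introduction presents a program "using a within-group peer coaching intervention to improve outcomes for older adults at risk for falls". Under Self-Assessment, "If they report barriers, then the group can help with group problem solving, by practicing brainstorming". The Peer-Coaching Component says that "The emphasis of the LIFT program is on learning adherence and peer support skills together". The 12-week goals add that "Participants will connect via phone or social media 1-2x weekly with a member of their peer coaching team".

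For structure, Aim 3 concerns "preliminary efficacy of the LIFT Fall Prevention program among 48 patients within an outpatient physical therapy practice". Under Enrollment, "the start date is to be determined when all 16 participants have been enrolled", and the Randomization section assigns each set of 16 individually. The program content table splits the LIFT class into two teams of four at Class 7, in week 5.

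Controls continue with one-on-one physical therapy, and "they will attend a control group class that provides social interaction and interesting health information".

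**The concern.** Patients are randomized one by one, but LIFT patients are then treated together. If group problem solving and peer coaching work as intended, members of a class may do well or badly together, and their post-test scores would be positively correlated. Each extra member of a class then adds less information than an independent patient would. An ordinary ANCOVA does not know this, so its standard error for the arm difference is too small and its interval too narrow.

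What is at stake is how precise the preliminary arm differences appear to those who plan the next study. No confirmatory decision depends on them. Enrollment, attendance and completion (Aim 1) are not touched. Baseline values are unaffected, and the residual SD is nearly unbiased.

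**Working it through.** The plan has no power calculation, ICC or design effect to reproduce, so the check starts from its structure.

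**Inputs from the documents**
- 48 patients (Aim 3) in sets of 16 (Enrollment, Randomization): 48/16 = 3 waves. The staff-training text, which refers to a second and a third class session, agrees.
- Two teams of four in a LIFT class (program content, Class 7): 2 x 4 = 8 per class. This matches 16/2 = 8 if allocation is 1:1.

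**Assumptions**
- 1:1 allocation, so 24 per arm in 3 classes of 8.
- Two-sided 95% interval.
- ICC, as a share of residual variance, of 0.01, 0.05 or 0.10, in LIFT classes only.

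**Variance factor.** With residual variance s², n per arm and m per LIFT class, the LIFT mean has variance (s²/n) x (1 + (m-1) x ICC) and the control mean s²/n. Their sum divided by the independent value 2s²/n is

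factor = 1 + ICC x (m-1)/2, which is 1 + 3.5 x ICC for m = 8.

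**Coverage.** With treatment, pretest, age and sex fitted, the residual df are 48 - 5 = 43 and the critical value is 2.017. Approximate coverage is 2 x P(t43 < 2.017/sqrt(factor)) - 1. A simulation of the same ANCOVA (40,000 runs per cell, pretest correlation 0.6 assumed, Monte Carlo error 0.1 to 0.2 points) checks the formula.

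| ICC | factor | sqrt(factor) | coverage, formula | coverage, simulated |
|---|---|---|---|---|
| 0.01 | 1.035 | 1.017 | 94.6% | 94.5% |
| 0.05 | 1.175 | 1.084 | 93.0% | 93.1% |
| 0.10 | 1.350 | 1.162 | 91.0% | 91.1% |

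Multiplying the standard error by sqrt(factor) brings simulated coverage back to 94.9%, 95.0% and 95.0%.

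**Fewer analysed.** With 6 per class (assumed), the factor is 1 + 2.5 x ICC, and simulated coverage is 93.6% and 92.2% at ICC 0.05 and 0.10.

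**Teams only.** If correlation exists only within teams of 4, the factor is 1 + 1.5 x ICC. At ICC 0.05 and 0.10 the true standard error is 3.7% and 7.2% larger, and coverage is 94.3% and 93.4%.

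**Can the trial estimate the ICC?** No. An observed ICC of 0.05 from 3 LIFT classes of 8 (2 and 21 df) has a 95% interval of 0 to 0.87, with the negative limit set to 0. A comparison of 3 with 3 class means has 4 df and a critical value of 2.78.

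**Wave.** A wave effect shared by both arms cancels from the arm difference, so omitting it makes the interval slightly too wide. At an assumed wave SD of 0.3 residual SD and no clustering, the interval is 2.7% wider than with wave fitted, and coverage is 95.4%. With LIFT classes also clustering, coverage without wave is 95.2%, 93.7% and 91.9% at the three ICCs, so the omission partly masks the clustering. With wave fitted (runs without a wave effect), coverage is 94.6%, 93.1% and 90.8%. Fitting wave therefore does not cure it.

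**The case against.** The strongest reply is that this is a pilot, declared unpowered, with no ICC in the documents, so the size of the problem is entirely assumed. At ICC 0.05 the loss is about two points of coverage, for an interval that the SAP does not explicitly promise. This stands, and it sets the severity.

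Two further arguments stand in part. First, peer coaching aims at exercise adherence, which is not in the baseline table, so a pretest-adjusted ANCOVA does not directly fit the outcome where correlation is most plausible. The balance, gait and chair-stand tests follow individually tailored exercise. Barriers Self-Efficacy does have a pretest, though, and group problem solving runs throughout the classes, so correlation in the analysed outcomes cannot be dismissed. Second, teams are introduced only in week 5, so team-level correlation should be small at the 6-week test. That is why the calculation rests on classes and not on teams.

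The Feasibility Data section names one class instructor per arm. If that person leads every wave, instructor differences add no between-class variance within an arm. Group composition and peer effects remain.

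Two stronger readings are tempting. A reader might infer that both arms cluster equally. The factor would then be 1 + 7 x ICC, with coverage of 91.1% and 86.9% at ICC 0.05 and 0.10. The documents support this less well: the control class is educational and control therapy is one-on-one. A reader might also infer that a later formal trial will be too small. That would follow only if it were sized without a design effect, and the documents nowhere say so.

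**Conclusion.** The point holds, and it is minor. The ANCOVA has no term for group delivery, and the SAP does not acknowledge the issue. If outcomes correlate within LIFT classes, the reported standard error of the arm difference is too small. The shortfall is negligible at an ICC of 0.01 and modest at 0.05 to 0.10, as tabulated above.

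This rests on 1:1 allocation, classes of 8, ICCs that no document supplies, and clustering confined to the LIFT arm. The direction follows from any positive correlation within LIFT classes; the size does not. The documents do not show that such correlation will occur, only that the intervention's design makes it plausible.

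**What to change.** **1. Sensitivity interval.** Keep the planned ANCOVA as the main analysis and report the arm difference with a 95% confidence interval. Suggested SAP text: *Outcomes may correlate within LIFT classes. For each outcome and time point, one sensitivity interval will be given with the standard error of the arm difference multiplied by sqrt(1 + ICC x (m-1)/2), where m is the mean number analysed per LIFT class, at an assumed ICC of 0.05, with 0.10 as the upper case. Three classes per arm are too few to estimate an ICC or to fit a reliable class random-effects model.*

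This costs a few lines of wording and code and changes nothing in conduct. With m = 8 the sensitivity interval is 8% wider at ICC 0.05 and 16% wider at 0.10. It over-corrects if only teams cluster (95.9% and 96.6% coverage) and under-corrects if control classes cluster equally (93.4% and 92.0%).

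**2. Wave, as a separate precision point.** Fit randomization wave (fixed effect), age and sex with the pretest score in every ANCOVA. Wave costs 2 df. The interval is under 0.5% wider if there is no wave effect and about 3% narrower at an assumed wave SD of 0.3 residual SD. This does not replace item 1.
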